Circulating soluble factors (plasma, not applicable for China)		X n	X n	X n	X n	X n,t		8.8		
Stool sample collection for microbiome analysis (optional, applicable in North America and Europe only) u		X		X				8.8		
EORTC QLQ-LC13 (by e-device) v		X	first 8 weeks from	Weekly (±1 day on weeks 1, 2, 3, 5, 6, and 7, and ±3 days on weeks 4 and 8) for the first 8 weeks from randomization and then every 4 weeks (±3 days) relative to randomization until study termination or PFS2 or death						
EORTC QLQ-C30 (by e-device) v		X	Every 4 weeks (±3 da	• /	lomization until stu death	ıdy termination or P	FS2 or	8.1.3		
PRO-CTCAE (by e-device) v		X	Weekly (±1 day on we 12) for the first 12 wee to rando	ks from randomiza		y 4 weeks (±3 days)		8.1.3		
PGIS (by e-device) v		X	Every 8 weeks (±3 da	• /	lomization until stu death	idy termination or P	FS2 or	8.1.3		
EQ-5D-5L (by e-device) v		X	Every 8 weeks (±3 da	• /	lomization until stu death	ıdy termination or P	FS2 or	8.1.3		
Health resource use module (HOSPAD)	X	]	Every 24 weeks (±3 days)	) relative to randon	nization until treatr	nent discontinuation	1	8.9		
Mandatory tumor tissue sample c	X							5.1, 8.8		
Optional newly acquired tumor biopsy c	X							5.1, 8.8		
Genetic sample (optional DNA element for long-term storage/future use, not applicable for China) w		X						8.7		

Week	Screening a -6 to -1	C1 0		C3 less dosing needs t			C26/ Final Dosi ng Visit	For details,			
Day	-42 to -1	1 b	1b q28days ±3 days unless dosing needs to be held for toxicity reasons 701								
Efficacy evaluations											
Tumor assessments (CT or MRI) (RECIST 1.1) y	X²	randomi and the radiolo the next	study tumor assessments zation), followed by q12 en q24w ±1w thereafter (gical progression, plus or regularly scheduled imany delays in dosing. Tum	w ±1w until up to 9 relative to the date ne follow-up scan r ging visit. This on-	96 weeks relative to of randomization) no earlier than 4 we study schedule MU to progression may	o the date of randon until RECIST 1.1-d ceks later and no lat JST be followed reg	nization, lefined er than gardless	8.1			

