3.2.9 Best objective response (BoR)

BoR is calculated based on the overall visit responses from each RECIST assessment. It is the best response a patient has had following randomization but prior to starting any subsequent anticancer therapy (excluding radiotherapy) and up to and including RECIST progression or the last assessment in the absence of RECIST progression and subsequent cancer therapy.

Categorization of BoR will be based on RECIST using the following response categories: CR, PR, SD, PD and NE.

For determination of a best response of SD, the earliest of the dates contributing towards a particular overall visit assessment will be used. SD should be recorded at least 8 weeks minus 1 week, i.e. at least 49 days (to allow for an early assessment within the assessment window), after randomization (i.e. study day 50). For CR/PR, the initial overall visit assessment which showed a response will use the latest of the dates contributing towards a particular overall visit assessment.

BoR will be determined programmatically based on RECIST from the overall visit response using all BICR data up until the first progression event, the start of subsequent cancer therapy or the last assessment in the absence of progression/subsequent cancer therapy. The denominator will be consistent with that used in the ORR analysis. In particular, patients with no evidence of disease will be excluded.

For patients whose PFS event is death, BoR will be calculated based upon all evaluable RECIST assessments prior to death.

For patients who die with no evaluable RECIST assessments, if the death occurs \leq 119 days (i.e. 2 x 8 weeks + 1 week to allow for a late assessment within the assessment window) after randomization, then BoR will be assigned to the progression (PD) category. For patients who die with no evaluable RECIST assessments, if the death occurs >119 days (i.e. 2 x 8 weeks + 1 week) after randomization then BoR will be assigned to the NE category.

A patient will be classified as a responder if the RECIST criteria for a CR or PR are satisfied at any time following randomization, prior to RECIST progression and prior to starting any subsequent cancer therapy.

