3.3.1.1 Time to QLQ-C30 and QLQ-LC13 symptom deterioration

For each of the symptoms scales/items in the QLQ-C30 and QLQ-LC13, time to symptom deterioration will be defined as the time from randomization until the date of the first clinically meaningful symptom deterioration (an increase in the score from baseline of \geq 10) that is confirmed at the next available assessment at least 14 days apart or death (by any cause) in the absence of a clinically meaningful symptom deterioration, regardless of whether the patient withdraws from study treatment or receives another anticancer therapy prior to symptom deterioration (i.e. date of symptom deterioration event or censoring – date of randomization + 1). Missed visits are allowed in between assessments confirming deterioration. This is considered a conservative approach whereby a deterioration is considered a 'negative' outcome and therefore should be assigned as such, regardless of missed visits.

Death will be included as an event only if the death occurs within 2 visits of the last PRO assessment (and where there were no previous 2 consecutive missed visits) where the symptom change could be evaluated. Patients with a single deterioration and no further assessments will be treated as deteriorated in the analysis.

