3.3.1.3 QLQ-C30 and QLQ-LC13 symptom improvement rate

The symptom improvement rate will be defined as the number (%) of patients with a minimum of 2 consecutive assessments at least 14 days apart that show a clinically meaningful improvement (a decrease from baseline score ≥ 10 for symptom scales/items) in that symptom from baseline. Missed visits are not allowed in between consecutive assessments of improvement. This is considered a conservative approach whereby an

improvement is considered a 'positive' outcome and therefore for any avoidance of doubt in the assessment of an improvement, missed visits are not allowed.

When the assessment schedule is weekly i.e. QLQ-LC13 weeks 1 to 8, an improvement needs to be observed at each assessment that falls within the 14 day interval to be classed as an improvement. For example:

V1	V2	V3	V4	Outcome
(Week 1)	(Week 2)	(Week 3)	(Week 4)	
IMP	IMP	IMP	NC	Improvement
IMP	IMP	NC	DT	No improvement*
IMP	MV	IMP	IMP	No improvement*
NC	IMP	NC	IMP	No improvement*

DT Deterioration; IMP Improvement; MV Missed visit. NC No change.

The denominator will consist of a subset of the FAS who have a baseline symptom score ≥ 10 .

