 For any scan > day 847 (week 121) the visit schedule is q24w±1 week and thus the maximum time between two consecutive scans is 1+24+24+1=50 weeks (350 days).

Table 10 2 Missed Visits – RECIST

ePRO Assessments

As per Sections 3.3.1.1 and 3.3.1.2, confirmation of deterioration will first be determined, then the censoring rules will be applied to assess if any determined deterioration can be used or if it needs to be censored earlier due to 2 consecutive missed visits. For ePRO assessments, we will apply a 'look-forward' approach to the 2 missed visit rule.

For example:

Baseline	V1	V2	V3	V4	V5	V6	V7	V8	Observed confirmed deterioration visit*	Time to deterioration derivation
	NC	DT	DT	NC	MV	NC	IMP	NC	Event at V2	Event at V2
	MV	MV	NC	DT	MV	DT	DT	NC	Event at V4	No event, censor at baseline (due to 2 missed visits)
	MV	DT	NC	MV	MV	DT	DT	NC	Event at V6	No event, censor at V3 (due to 2 missed visits)
	NC	DT	NC	MV	IMP	DT	NC	DT	Event not confirmed, bit if this is the last DT prior to DCO and then it is counted as confirmed at V8	Event at V8
	NC	DT	NC	MV	IMP	DT	MV	DT	Event at V6	Event at V6
	NC	IMP	NC	IMP	MV	MV	IMP	DT	Event at V8, if last visit prior to DCO	No event, censor at V4 (due to 2 missed visits)
	MV	MV	NC	MV	MV	DT	DT	NC	Event at V6	No event, censor at

									baseline (due to 2 missed visits)
NC	DT	MV	MV	DT	NC	IMP	DT	Event at V2	Event at V2

DT Deterioration; IMP Improvement; MV Missed visit. NC No change.

Length of 2 missed visit window for EORTC QLQ-LC13

The scheduled visit assessments and visit windows for the QLQ-LC13 are weekly (± 1 day on weeks 1, 2, 3, 5, 6 and 7 and ± 3 days on weeks 4 and 8) for the first 8 weeks from randomization and then every 4 weeks relative to randomization until study termination, PFS2 or death.

Missing baseline or within 2 visits of baseline:

- A patient without baseline will be censored at day 1 unless they die \leq day 15.
- Any assessment \leq day 15 (2 weeks + 1 day) is within 2 visits of baseline and therefore cannot be censored for missing visits.

Schedule: $q1w \pm 1 day$:

• For any assessments > day 1 where the visit schedule is q1w \pm 1 day, the maximum time between two consecutive assessments is 1+7+7+1=16 days

Schedule: $q1w \pm 3$ days:

• For any assessments where the visit schedule changes from $q1w \pm 1$ day to $q1w \pm 3$ days, the maximum time between two consecutive assessments is 1+7+7+3=18 days

Schedule: $q4w \pm 3$ days:

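### The 14-day confirmation rule for weekly QLQ-LC13 diaries has no allowance for the completion windows and can contradict the SAP's own worked example

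*SAP*

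**What the plan says.** SAP 3.3.1.3 defines symptom improvement by "a minimum of 2 consecutive assessments at least 14 days apart that show a clinically meaningful improvement". For the weekly phase ("When the assessment schedule is weekly i.e. QLQ-LC13 weeks 1 to 8") it adds that "an improvement needs to be observed at each assessment that falls within the 14 day interval to be classed as an improvement", and missed visits in between are not allowed. An example table laid out by week, without dates, classes improvement at weeks 1, 2 and 3 followed by no change at week 4 as an improvement.

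SAP 3.3.1.1 requires a first deterioration to be "confirmed at the next available assessment at least 14 days apart". Here missed visits are allowed, and a single deterioration with no later assessment counts as an event.

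The QLQ-LC13 schedule in Table 1 of Protocol 1.1 is "Weekly (±1 day on weeks 1, 2, 3, 5, 6, and 7, and ±3 days on weeks 4 and 8") for the first 8 weeks, then every 4 weeks ±3 days. SAP Appendix B repeats these windows ("The scheduled visit assessments and visit windows for the QLQ-LC13 are weekly") and builds them into the missed-visit rule: "the maximum time between two consecutive assessments is 1+7+7+1=16 days". A footnote there says that the 14 days for confirming deterioration should take account of the weekly schedule. It gives no number and does not mention improvement.

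Elsewhere the SAP does allow for windows. For a best response of stable disease, SAP 3.2.9 states: "SD should be recorded at least 8 weeks minus 1 week, i.e. at least 49 days (to allow for an early assessment".

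**The concern.** The 14-day minimum is the same as the scheduled distance between weekly diaries n and n+2. Any pair in which the second diary is done slightly earlier within its window than the first falls short, although the patient kept to the schedule. The text and the example table can then give different answers for the same patient, and two programmers working from the same section could produce different results.

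Three of the five PRO measures named as primary (cough, dyspnea and chest pain) come from the QLQ-LC13. Improvement rate and time to deterioration are both formally compared between arms for these scales. What is at stake is misclassification of some patients in these two analyses.

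**Working it through.** **Inputs.** Windows: ±1 day at weeks 1, 2, 3, 5, 6 and 7; ±3 days at weeks 4 and 8 (Protocol Table 1; SAP Appendix B). Minimum gap: 14 days (SAP 3.3.1.1, 3.3.1.3). Nominal study days 8, 15, 22 and 29 for weeks 1 to 4 (the weekly example in SAP Table 8). The distribution of completion days within the window is not in the documents, so it is an assumption and is varied below.

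**Formula.** Let x and y be the offsets in days of diaries n and n+2 from their nominal days. The gap is 14 + y − x, and the pair fails when y < x.

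**Reproducing the SAP's figures.** The maximum gap is 1+7+7+1 = 16 days with two ±1-day windows and 1+7+7+3 = 18 days when one window is ±3. Both match Appendix B.

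**The minimum by the same arithmetic.** 14 − 1 − 1 = 12 days for pairs 1-3, 3-5 and 5-7; 14 − 1 − 3 = 10 days for pairs 2-4, 4-6 and 6-8.

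**Against the SAP's example.** Diaries on day 9 (week 1, one day late), day 15 (week 2) and day 21 (week 3, one day early) are all in window. The span is 21 − 9 = 12 days. With improvement at all three, no change at week 4 and no later qualifying run, the date rule gives no improvement; the table gives improvement.

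**Share of n to n+2 pairs that fail.**
- Independent and uniform within the window: 3 of 9 offset pairs = 33.3% (±1/±1); 9 of 21 = 42.9% (week 4 or 8 involved).
- Share p on the nominal day, the rest spread evenly. For ±1/±1, with q = (1 − p)/2, the failure probability is 2pq + q². At p = 0.90: 2 × 0.90 × 0.05 + 0.05² = 9.25%. At p = 0.95: 2 × 0.95 × 0.025 + 0.025² = 4.8%. Enumerating the mixed windows gives 9.4% and 4.9%.
- Always the same weekday: y = x, so 0%.

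**What is not affected.** Diaries n and n+3 are at least 21 − 1 − 3 = 17 days apart, so a run of four weekly diaries always passes. Weeks 8 to 12 and all 4-weekly pairs are at least 28 − 3 − 3 = 22 days apart, which clears the later QLQ-LC13 and all of the QLQ-C30. The MMRM in SAP 4.2.11.1 uses no confirmation rule.

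**Deterioration (DT; NC = no change).** If n+2 falls short, n+3 becomes the confirming diary (week 12 if n is week 6). DT-DT-DT-NC then loses the event at n. DT-DT-NC-DT gains an event at n that week n+2 would have refused; by schedule, the earliest event in that pattern would be n+1, confirmed at n+3. A lasting deterioration is confirmed either way and keeps its original date.

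**Candidate remedies (uniform assumption).**
- 12-day floor: no ±1/±1 pair fails, but 3/21 = 14.3% of pairs involving week 4 or 8 still do. Adjacent diaries cannot pass, since their maximum gap is 7+1+3 = 11 days.
- 10-day floor: no n to n+2 pair fails, but adjacent diaries 3-4, 4-5 and 7-8 pass in 3/21 = 14.3% of cases.
- Scheduled visits: no failures and no false passes.

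**The case against.** The strongest reply is that strictness is deliberate. SAP 3.3.1.3 describes its handling of improvement as conservative, and diaries 12 days apart have not shown 14 days of improvement. The stable-disease rule is also a different case, because it lets a single early scan count. In addition, the example table is set out by scheduled week and the Appendix B footnote points to the weekly schedule, so a programmer might already read the rule by schedule.

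Part of this stands. The footnote and table do suggest a schedule-based intention. But the footnote gives no tolerance and covers only deterioration, the rule itself is written in days, and SAP 4.1.2 places assessments in visit windows by actual rather than intended date. If 14 elapsed days are really wanted, the example table is incomplete.

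A reader might also infer that in-window diaries often fail, that confirmed deteriorations are delayed or removed, or that treatment differences are attenuated. The documents support none of these as stated. They give no completion pattern. The deterioration error runs in both directions. The windows are the same in all arms, and no effect on a treatment comparison has been shown.

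**Conclusion.** The point holds in a limited form. In weeks 1 to 8 the 14-day minimum has no window allowance, so diaries completed as scheduled can fail it, and the result can contradict the SAP's own table. The proportion of n to n+2 pairs affected ranges from 0% through about 5% to 9% up to 33% to 43%, depending entirely on the assumed completion pattern. These are shares of diary pairs, not of patients. For improvement, only a run of exactly three weekly diaries is lost, and the patient is misclassified only if no later run qualifies.

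It would be wrong to read this as a threat to the main PRO analysis or to the primary tests. Protocol 9.5.1.9 makes the MMRM the primary PRO analysis, and the multiple testing procedure in SAP 4.2.1 covers only PFS and OS. The case for a change is the internal conflict and the low cost of removing it, not a large numerical effect.

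**What to change.** In SAP 3.3.1.1, 3.3.1.3 and Appendix B, define confirmation in the weekly phase by scheduled visit: the confirming diary must belong to a scheduled assessment at least two weeks later by schedule. For improvement this means diaries n, n+1 and n+2 all improved, as the example table already shows. Do not substitute a 10-day floor, because it would let adjacent weekly diaries around weeks 4 and 8 confirm each other. The QLQ-C30 rules need no change.

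The cost is about one sentence in each place and no new data. The downside is that confirmation may rest on diaries 10 to 13 actual days apart, which the SAP should state.

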3.3.1.4 QLQ-C30 GHS/QoL/functional improvement rate

The GHS/QoL/functional improvement rate will be defined as the number (%) of patients with 2 consecutive assessments at least 14 days apart that show a clinically meaningful improvement (an increase from baseline score ≥10 for functional scales and GHS/QoL) in that scale from baseline. Missed visits are not allowed in between consecutive assessments of improvement. This is considered a conservative approach whereby an improvement is considered a 'positive' outcome and therefore for any avoidance of doubt in the assessment of an improvement, missed visits are not allowed.

The denominator will consist of a subset of the FAS who have a baseline score <90.

3.3.2 EQ-5D-5L

The EQ-5D-5L is a standardized measure of health status developed by the EuroQol Group in order to provide a simple, generic measure of health for clinical and economic appraisal. Applicable to a wide range of health conditions and treatments, it provides a simple descriptive profile and a single index value for health status that can be used in the clinical and economic evaluation of health care.

The EQ-5D-5L index comprises six questions that cover five dimensions of health (mobility, self-care, usual activities, pain/discomfort and anxiety/depression) and a global health status

^{*}Assuming no further assessments.

visual analog scale (VAS). For each dimension, respondents select which statement best describes their health on that day from a possible 5 options of increasing levels of severity (no problems, slight problems, moderate problems, severe problems and unable to/extreme problems). A unique EQ-5D-5L health state is referred to by a 5-digit code allowing for a total of 3125 health states. For example, state 11111 indicates no problems on any of the 5 dimensions. These data will be converted into a weighted health state index by applying scores from EQ-5D-5L value sets elicited from general population samples (the base case will be the United Kingdom valuation set, with other country value sets applied in scenario analyses). Where values sets are not available, the EQ-5D-5L to EQ-5D-3L crosswalk (Oemar and Janseen 2013) will be applied. In addition to the descriptive system, respondents also assess their health on the day of assessment on a visual analogue scale, ranging from 0 (worst imaginable health) to 100 (best imaginable health). This score is reported separately.

The evaluable population will comprise a subset of the FAS who have a baseline EQ-5D-5L assessment.

3.3.3 PGIS

The PGIS item is included to assess how a patient perceives his/her overall current severity of cancer symptoms. Patients will choose from response options including: "no symptoms", "very mild", "mild", "moderate", "severe" and "very severe". For summaries of the "overall" score, "overall" will present the best post-baseline response over all time points, ranked from best (i.e. "no symptoms"), to worst (i.e. "very severe").

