1.1.4 Exploratory objectives

Exploratory objectives*:	Endpoint/variables:
To assess treatment-related side effects in patients treated with durvalumab monotherapy and durvalumab and tremelimumab combination therapy compared to placebo using PRO-CTCAE	Change in the 9 treatment-related symptoms evaluated in this study
To assess the patients' overall impression of the severity of their cancer symptoms using PGIS	PGIS: Proportion of patients assessing current symptom severity
To describe and evaluate health resource use associated with durvalumab monotherapy and durvalumab and tremelimumab combination therapy and underlying disease	Health resource utilization measures including hospitalization, outpatient visits, or emergency department visits
To explore the impact of treatment and disease state on health state utility using the EQ-5D-5L	The EQ-5D-5L health state utility index will be used to derive health state utility based on patient-reported data

Exploratory objectives*:

To collect blood and tissue samples, or leverage residual samples, for analysis of peripheral and tumoral biomarkers (not applicable to China)

To investigate the relationship between TMB measured in tumor and/or blood and efficacy outcomes with durvalumab monotherapy and durvalumab and tremelimumab combination therapy (TMB-related testing or analysis will not be conducted on samples from China)

To explore the relationship(s) between patient biomarker status and durvalumab PK exposure and clinical outcomes before and after treatment (TMB related testing or analysis will not be conducted on samples from China)

To explore irRECIST as assessment methodologies for clinical benefit of durvalumab monotherapy and durvalumab and tremelimumab combination therapy compared to placebo with assessment by BICR

To collect and store DNA from tissue and/or blood according to each country's local and ethical procedures for future exploratory research into genes/genetic variation that may influence response (i.e. distribution, safety, tolerability, and efficacy) to IPs and/or susceptibility to disease (optional, not applicable for China)

To investigate the effect of baseline colonic microbiome on response to treatment and the effect of treatment on the microbiome over time (applicable for EU and North America only)

Endpoint/variables:

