3.3 Patient Reported Outcome (PRO) Variables

PRO variables will be assessed using the European Organization for Research and Treatment of Cancer (EORTC) 30-item core quality of life questionnaire (QLQ-C30) with the lung cancer module (QLQ-LC-13) (health-related quality of life [HRQoL] with lung cancer specific additional concerns), EQ-5D-5L, Patient's Global Impression of Severity (PGIS), and PRO-CTCAE. All items/questionnaires will be scored according to published scoring guidelines or the developer's guidelines, if published guidelines are not available. All PRO analyses will be based on the FAS, unless otherwise stated. PRO questionnaires will be collected as per the assessment schedule in Table 1 of the CSP, up until study termination, PFS2 (as defined in Section 3.2.8) or death. Rules for handling multiple records are detailed in Section 4.1.2.

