Endpoints Analyzed	Notes
Objective response rate	Cochran-Mantel-Haenszel (CMH) test for difference in proportions using BICR assessments (RECIST 1.1) adjusting for the same factors as the primary endpoint for:
	 Secondary analysis (durvalumab monotherapy and durvalumab + tremelimumab combination therapy versus placebo and durvalumab monotherapy versus durvalumab + tremelimumab)
	Sensitivity analysis using CMH test repeated using the site Investigator assessments (RECIST 1.1)
Duration of response	Kaplan-Meier estimates and confidence intervals
PFS at 18 months and 24 months	Kaplan-Meier estimates and confidence intervals
Time to death or distant metastasis	Stratified log-rank test using BICR assessments (RECIST 1.1)
OS at 24 and 36 months	Kaplan-Meier estimates of survival at 24 months and 36 months and analyses following the method described by Klein et al (Klein et al 2008, Klein et al 2007)
Time from randomization to second progression	Stratified log-rank test using site Investigator assessments
Change from baseline in key symptoms (EORTC QLQ-C30 and QLQ-LC13)	Mixed-model repeated measures analysis
GHS/QoL/Function improvement rate (EORTC QLQ-C30 endpoints)	Logistic regression
Symptom improvement rate (EORTC QLQ-C30 and QLQ-LC13 endpoints)	Logistic regression
Time to GHS/QoL/Function deterioration (EORTC QLQ-C30 endpoints)	Stratified log-rank test
Time to symptom deterioration (EORTC QLQ-C30 and QLQ-LC13 endpoints)	Stratified log-rank test
Treatment-related symptoms (PRO-CTCAE and PGIS)	Presented using summaries and descriptive statistics

BICR Blinded Independent Central Review; CTCAE Common Terminology Criteria for Adverse Event; EORTC European Organisation for Research and Treatment of Cancer; GHS/QoL Global health score/Quality of life; ORR Objective response rate; OS Overall survival; PFS Progression-free survival; PGIS Patient's Global Impression of Severity; PRO Patient-reported outcome; QLQ-C30 30-Item core quality of life questionnaire; QLQ-LC13 Lung cancer module.

[figure not shown]

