4.2.11.3 PGIS

The number and percentage of patients in each category of the PGIS responses will be summarized by treatment group, at each assessment time point and overall.

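### The PGIS 'overall' row takes each patient's best post-baseline answer with no fixed window, so at equal symptom burden it can only stay level or favour the arm followed longer

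*SAP*

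**What the plan says.** SAP 3.3.3 gives PGIS six ordered categories, from 'no symptoms' to 'very severe', and says that the 'overall' score "will present the best post-baseline response over all time points". SAP 4.2.11.3 says that the number and percentage of patients in each category "will be summarized by treatment group, at each assessment time point and overall".

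The protocol's schedule of activities (Tables 1 and 2) asks for PGIS every 8 weeks from randomization. SAP 3.3 says that PRO questionnaires are collected "up until study termination, PFS2 (as defined in Section 3.2.8) or death".

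PGIS is an exploratory objective (SAP 1.1.4), with the endpoint "PGIS: Proportion of patients assessing current symptom severity". SAP Table 7 gives its analysis as "Presented using summaries and descriptive statistics". It lies outside the multiple testing procedure.

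**The concern.** A best-of-K summary improves mechanically with K, the number of answers. Here K is set by time to PFS2, death or study termination, and the trial is designed on the expectation that durvalumab delays progression and death. If it does, durvalumab patients answer more often, and the 'overall' row gives them more chances to record one good category. The item in protocol Appendix H asks about symptoms today, so a single good day fixes a patient's result. Any deterioration after that day is invisible in the row.

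Elsewhere the SAP guards against both features. The QLQ-C30 and QLQ-LC13 improvement rates need two consecutive improved assessments at least 14 days apart with no missed visit between them (SAP 3.3.1.3 and 3.3.1.4). The mixed-model comparison stops at progression, death or 24 months (SAP 4.2.11.1). The PGIS 'overall' row has neither safeguard.

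At stake is a between-arm contrast, in a row that a reader may well quote because of its label, which mixes length of follow-up with symptom severity.

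**Working it through.** **What the documents supply.** Neither document gives a figure for PGIS 'overall' or for time to PFS2. The protocol synopsis gives assumed medians of 15.4 versus 10 months for PFS and 32.9 versus 24 months for OS. Under exponential times these agree with the stated hazard ratios: 10/0.65 = 15.4 and 24/0.73 = 32.9. PFS2 falls between first progression and death, so the two pairs of medians serve as brackets for the end of PGIS collection.

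**What has to be assumed.** The chance p of 'no symptoms' at a visit is the same in both arms and constant over time. It averages 30% and varies between patients as Beta(0.3, 0.7), Beta(0.6, 1.4) or Beta(1.5, 3.5), from strong to weak within-patient correlation. Follow-up is exponential with an administrative cap of 24, 36 or 60 months. Patients with at least one post-baseline answer are counted.

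**Formulas.** The visit interval is 56/30.4375 = 1.84 months. With rate λ = ln 2/median, P(K ≥ k) = exp(−1.84 λk), up to the last visit before the cap. Given k answers, P(best = 'no symptoms') = 1 − B(a, b+k)/B(a, b), where B is the beta function. This is averaged over K ≥ 1 in each arm, and the arms are subtracted.

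**Check of the conditional formula.** For Beta(1.5, 3.5) and k = 6, the chance of never answering 'no symptoms' is (3.5/5)(4.5/6)(5.5/7)(6.5/8)(7.5/9)(8.5/10) = 0.237, so the probability is 0.763. Multiplying by (9.5/11)(10.5/12)(11.5/13) gives 0.159 for k = 9, so the probability is 0.841. More answers raise the result with p unchanged.

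**Results.** Spurious difference, durvalumab minus placebo, in percentage points:

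| End of follow-up | Cap (months) | Mean answers, placebo vs durvalumab | Beta(0.3, 0.7) | Beta(1.5, 3.5) |
|---|---|---|---|---|
| PFS medians | 24 | 6.8 vs 8.3 | 3.2 | 5.5 |
| PFS medians | 36 | 7.6 vs 10.0 | 3.8 | 6.0 |
| PFS medians | 60 | 8.2 vs 11.7 | 4.2 | 6.3 |
| OS medians | 24 | 9.6 vs 10.4 | 1.4 | 2.4 |
| OS medians | 36 | 12.3 vs 13.7 | 1.8 | 2.8 |
| OS medians | 60 | 15.8 vs 18.7 | 2.4 | 3.2 |

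Beta(0.6, 1.4) falls between the two columns throughout. As an example of the levels, at the PFS medians with a 36-month cap and Beta(1.5, 3.5), the shares are 70.3% on placebo and 76.3% on durvalumab.

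**Sensitivity to the assumed rate.** With average p from 5% to 40%, independent to strongly correlated visits and the same caps and brackets, the difference runs from 0.5 to 10.0 points. The top of that range needs a 10% rate and independent visits. The sign never changes. With equal follow-up the difference is exactly 0.

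**Effect of a common window.** At the PFS medians and a 30% average rate, the difference is 0.85 to 1.52 points for a 6-month window, 1.90 to 3.48 for 12 months and 3.24 to 5.48 for 24 months. A window shrinks the effect without removing it, because some patients still leave before the window closes.

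**The case against.** The strongest reply is that nothing is decided on this row. PGIS is exploratory and descriptive, carries no test or confidence interval, and may be reported outside the CSR. The SAP states the definition openly, and best-over-time summaries are familiar: the SAP also uses them for best objective response and best change in tumour size. All of this stands, and it limits the weight of the point.

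Several stronger readings are tempting, and the documents do not support them.

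- A reader might infer that follow-up for PGIS is unlimited. It ends at PFS2, death or study termination. What is missing is a fixed window, and the outcome-dependent stops are what create the imbalance.
- A reader might compare 6 answers (12 months) with 9 (18 months) and infer a false gap of 5 to 8 points. That gives every durvalumab patient 50% more answers, for which neither document gives a basis. With follow-up spread around the protocol's own medians the gap is smaller.
- A reader might infer that the row cannot show worsening at all. It can, if every post-baseline answer is worse than baseline. What it hides is deterioration after a good answer.
- A reader might infer that the exploratory objective is compromised. Its endpoint is current severity, which the by-visit table addresses directly. The 'overall' row is an addition to it.

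The constant chance per visit is also open to challenge. Patients enter within 42 days of chemoradiotherapy, and collection continues past first progression. If the best answers cluster early, late visits add little and the gap shrinks. The documents give no time course, so this remains an uncertainty about size. It does not change the direction.

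**Conclusion.** The point holds as a minor defect in the definition of one row. The direction is certain: with equal symptom burden, the longer-followed arm can only look the same or better. The size is about 1 to 6 percentage points under a constant 30% average chance of 'no symptoms' per visit, exponential follow-up and caps of 24 to 60 months. It is nearer the top if PGIS collection ends close to first progression and nearer the bottom if it ends close to death. The rate, the within-patient correlation and the timing of PFS2 are assumptions that the documents do not supply.

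No primary, key secondary or tested result is touched. The by-visit table does not have the best-of-K effect, although it remains conditional on patients who are still reporting.

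**What to change.** Delete the best-response 'overall' sentence in SAP 3.3.3 and the words 'and overall' in SAP 4.2.11.3, and keep the by-visit table as planned. This costs one sentence, two words and one table row, and needs no new data.

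If the sponsor prefers to keep the row, label it 'best post-baseline response', restrict it to a fixed common window, show the number of PGIS assessments per arm beside it, and note that the window reduces the effect without removing it. The assessment counts would need adding, because the compliance summaries in SAP 3.3.5 cover QLQ-C30, LC13 and EQ-5D-5L but not PGIS.

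A most-frequent or median category over the first 24 weeks is not a good substitute. At 8-weekly intervals it rests on about three answers, the most frequent category is undefined when all three differ, and with two answers the median can fall between categories.
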